## **PATIENT POPULATION**

In a 2:2:1 fashion, 90 subjects (group 1: n=36; group 2: n=36; group 3: n=18) will be randomized at UCLA Medical Center. Each subject will be followed for 6 months post-transplant.

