## **SECONDARY ENDPOINTS**

- Mean serum creatinine, eGFR (MDRD) at weeks 1, 2, 4, 8, 12, 16, 20 and 24
- 1, 3 month and 6 month cumulative incidence of acute allograft rejection episodes, steroid resistant rejection episodes, dialysis requirements
- Incidence of death and/or graft failure at 6 months
- Tolerability and side effect profile of the combination drug therapies
- Incidence of infectious complications
- Time to first episode of acute rejection
- Refractory rejection episodes (requiring immunosuppression beyond T cell depletion)
- Rejection episodes per subjects
- Number of subjects requiring full-dose calcineurin inhibitor rescue therapy
- Monitor CD25 cell count for 3 months
- Economic analysis to determine cost-effectiveness of induction therapy with IL-2 monoclonal antibody
- Economic analysis to determine cost-effectiveness of delayed therapy with mTOR

**A three arm, single center, randomized, prospective, pilot trial of induction and maintenance immunosuppression with basiliximab, delayed dose tacrolimus plus mycophenolate mofetil, and SOC corticosteroids versus immunosuppression with basiliximab, delayed dose tacrolimus plus mycophenolate mofetil, and SOC corticosteroids with delayed addition of everolimus and mycophenolate minimization versus standard dose tacrolimus and mycophenolate mofetil plus corticosteroids in patients undergoing orthotopic liver transplantation (OLT) with concomitant renal dysfunction**

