Official Title:

A Study in Adults on Pre-LT Dialysis With Basiliximab, Delayed Tacrolimus (TAC), Mycophenolate (MMF), and Steroids (Group 1) vs. Basiliximab, Delayed TAC, MMF, Steroids, With Everolimus 30 Days Post-LT (Group 2) vs. TAC, MMF, and Steroids (Group 3)

NCT Number:

NCT04104438

Document Date:

September 3, 2020

Statistical Analysis

Continuous variables were expressed as median (range) and were compared using the Mann-Whitney U test. Categorical variables were expressed as a numerical percentage and compared by the Chi-square test or the Fishers Exact Test. Survival curves were generated by the Kaplan-Meier method, and differences in survival rates were analyzed using the Log-Rank test. All tests were two-sided, and the significance level was $p<0.05$. All analyses were performed using IBM® SPSS® Statistics version 26 (IBM Corporation, Armonk, NY).

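### The SAP names only a two-sample test for continuous variables in a three-arm trial, with no named contrasts and no multiplicity rule, so the false-positive rate per endpoint and visit is about 8% to 12% under the likely pairwise readings, not 5%

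*SAP*

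**What the plan says.** The design has three arms. The title printed at the end of the protocol synopsis begins "A three arm, single center, randomized, prospective, pilot trial", and the Patient Population section gives the sizes: "In a 2:2:1 fashion, 90 subjects (group 1: n=36; group 2: n=36; group 3: n=18) will be randomized".

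The protocol's Statistical Analysis section is marked TBD, so the SAP's single paragraph is the whole analysis plan. It contains:

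- **Continuous data:** "Continuous variables were expressed as median (range) and were compared using the Mann-Whitney U test".
- **Categorical data:** "Categorical variables were expressed as a numerical percentage and compared by the Chi-square test or the Fishers Exact Test".
- **Time-to-event data:** "differences in survival rates were analyzed using the Log-Rank test".
- **Error level:** "All tests were two-sided, and the significance level was" p<0.05.

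Neither document says which arms are compared with which, names a three-group test for continuous data, or gives a multiplicity adjustment or testing order.

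**The concern.** Mann-Whitney U compares two groups. With three arms it gives a p-value only after someone picks two arms or pools some of them, and the SAP leaves that choice open. If several pairs are tested, each at 0.05, the chance of at least one false difference for that endpoint exceeds the level the SAP declares.

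Much of the trial's renal evidence is continuous. The protocol lists serum creatinine and eGFR at eight visits each, change in eGFR from the start of everolimus, and urinary protein/creatinine ratio. Lipids and CD25 counts are also continuous. A borderline result could be reported as a difference between arms, or not, depending on which pairs were looked at.

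The problem is separate from choosing a primary endpoint or time point, because it remains for one endpoint at one visit.

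**Working it through.** The documents state no power, sample-size derivation or family-wise error rate, so there is no such figure to reproduce. The allocation is consistent: 90 × 2/5 = 36, 90 × 2/5 = 36, 90 × 1/5 = 18.

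**Inputs.** From the protocol: arms of 36, 36 and 18. From the SAP: Mann-Whitney U, two-sided 0.05, no adjustment. Assumed: normal data with no true difference.

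**Step 1: reference values that ignore shared arms.**

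- Three independent tests: 1 − 0.95³ = 0.143. Bonferroni bound: 3 × 0.05 = 0.15.
- Two independent tests: 1 − 0.95² = 0.0975.

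**Step 2: allow for shared arms.** Pairs that share an arm are positively correlated, which lowers these values. In normal theory:

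- 1 v 3 and 2 v 3 (sharing Group 3): (1/18) / (1/36 + 1/18) = 0.67.
- 1 v 2 and 1 v 3 (sharing Group 1), in absolute value: (1/36) / √[(2/36)(3/36)] = 0.41.

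**Step 3: simulate the SAP's test.** For arms of size k and l, z = (U − kl/2) / √[kl(k+l+1)/12]. For 36 v 36 the mean is 648 and the SD √7884 = 88.8. For 36 v 18 the mean is 324 and the SD √2970 = 54.5. The three-group comparator is Kruskal-Wallis, H = 12/(90 × 91) × Σ(Rᵢ²/nᵢ) − 3 × 91, on 2 df.

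| Rule, one endpoint at one visit, no true difference | Any false positive |
|---|---|
| Each single pair (100,000 trials) | 4.8–5.1% |
| All three pairs, each at 0.05 | 12.0% (runs 11.4–12.2%) |
| Two comparisons with control, each at 0.05 | 8.5% (runs about 8–8.6%) |
| Groups 1 and 2 pooled v Group 3, one test | 4.9% |
| Kruskal-Wallis across three arms | 4.9% (runs 4.8–4.9%) |
| Kruskal-Wallis gate, then pairs at 0.05 | 4.9% (runs 4.8–4.9%) |
| Gate, but one pre-named pair tested at 0.05 outside it | 7.0–7.6% |

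A normal-theory check with 2,000,000 draws gives 12.1% for three pairs and 8.5% for two. Part of the spread between runs comes from the continuity correction. In one run of 100,000 trials, three pairs gave 12.2% without it and 11.8% with it.

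**Step 4: categorical endpoints, if run pairwise.** True event rates of 10%, 20% and 30% in all arms are assumptions; the documents give none.

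| Pairwise method | 10% | 20% | 30% |
|---|---|---|---|
| Uncorrected chi-square | 11.2% | 12.1% | 12.0% |
| Fisher if any expected count is below 5, else chi-square | 6.1% | 9.7% | 11.4% |
| Fisher throughout | 5.5% | 7.8% | 7.6% |
| Three-group chi-square | 4.5% | 4.9% | 5.1% |

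The expected-count rule is also an assumption, since the SAP gives none. At a 10% rate the control arm expects 18 × 0.10 = 1.8 events, the sparse setting where Fisher's test would normally be used and where inflation is smallest.

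**The case against.** The strongest reply is that the SAP does not commit to three pairwise tests. The synopsis objective compares the basiliximab regimens with standard triple therapy, which suggests two comparisons with control. Groups 1 and 2 also have the same listed regimen until about day 30, so at early visits pooling them against Group 3 would be one valid Mann-Whitney test at about 5%. This stands: 12% is the top of a range, not a certainty. It does not remove the point. The SAP names none of these options, two comparisons with control still give about 8% to 8.5%, and Group 2 v Group 1 is the contrast that isolates the everolimus strategy.

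A reader might also infer that the plan holds dialysis, rejection and survival to 5% while letting eGFR run at 12%. The documents do not support that. Chi-square, Fisher and log-rank can each take three groups, but the SAP does not say that they will. If they too are run pairwise, there is no difference in kind.

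Finally, the trial is called a pilot, and its stated primary objective (dialysis independence and time to it) is not a Mann-Whitney endpoint. This lowers the weight of the point. But the synopsis states its primary endpoint only as nephroprotection, without a measure, so it could include eGFR. The pilot label does not supply a three-arm test for creatinine or eGFR.

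**Conclusion.** The point holds as a gap in specification with a measurable consequence. For a continuous endpoint at one visit, the chance of at least one false difference is about 12% if all three pairs are tested and about 8% to 8.5% if only the control comparisons are, against about 5% for a three-group test. Categorical and survival tests can be inflated too if run pairwise, by less where Fisher's exact test is used on sparse data.

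The figures rest on the planned arm sizes, no true difference and normal data. They apply per endpoint and per visit. Creatinine and eGFR alone make 2 × 8 = 16 endpoint-visits, and the error across those is a separate matter.

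**What to change.** Replace the continuous-variable sentence in the SAP, and extend the categorical and survival sentences, with wording such as:

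> For each endpoint and time point, the three arms are first compared with a three-group test (Kruskal-Wallis; three-group chi-square or Fisher-Freeman-Halton; three-group log-rank) at two-sided 0.05. Only if this is significant are pairs of arms tested (Mann-Whitney; chi-square or Fisher; log-rank), each at two-sided 0.05. Otherwise pairwise results are reported descriptively.

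With exactly three arms this is a closed procedure, because any two pairwise nulls together imply the three-arm null. It holds the any-pair error for that endpoint and visit at about 5%. The SAP should add that error across endpoints and visits is not controlled. It should not let a pre-named pair be tested at 0.05 outside the gate, because the any-pair error then rises to about 7%.

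The change needs SAP wording and standard procedures only, with no new data or patients. The cost is some pairwise power. These figures assume a 0.8 SD shift, since the documents give no effect size:

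- **Groups 1 and 2 both shifted:** each comparison with control falls from about 75% to 68%.
- **Group 2 only shifted:** 2 v 1 falls from about 90% to 87%.

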## OBJECTIVES

To assess the efficacy and safety of basiliximab, delayed dose tacrolimus plus mycophenolate mofetil, and SOC corticosteroids versus basiliximab, delayed dose tacrolimus plus mycophenolate mofetil, and SOC corticosteroids and addition of delayed everolimus/mycophenolate minimization at one month post OLT compared to standard triple immunosuppression (tacrolimus, mycophenolate mofetil and corticosteroids) for prevention of acute organ rejection in liver transplant recipients with a high risk of developing renal dysfunction following OLT or with concomitant renal dysfunction prior to OLT.

**STUDY DESIGN:** single center, randomized, prospective, pilot

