Recently at our center, we completed a pilot trial in 60 adult OLT recipients in which we compared our standard triple immunosuppressive therapy with TAC plus myfortic and a standard of care corticosteroid taper to induction therapy with basiliximab with delayed use of tacrolimus therapy (until post-operative day 7), combined with myfortic and a rapid corticosteroid taper. The delay in tacrolimus therapy in the basiliximab induction group resulted in a mild improvement in renal function by three months following transplant while maintaining adequate immunosuppression to prevent acute rejection. This study was limited in the number of subjects enrolled and suffered from an inability to further reduce CNI exposure and perhaps enhance renal recovery or improvement following OLT. Thus additional CNI sparing agents could benefit these recipient with respect to enhancing renal function over time.

Everolimus is an mTOR inhibitor that is a structural derivative of sirolimus, with a distinct pharmacokinetic profile (shorter half-life and twice a day dosing). Clinical experience showed that a pharmacokinetic interaction of tacrolimus on everolimus may be less than with cyclosporine or even absent, and that the combination of everolimus and tacrolimus was safe and well tolerated with no new safety risks identified. [21, 22]

It has been approved for use in liver transplant recipients in combination with corticosteroids and reduced dose tacrolimus. Approval was based on a large study (n=719) in which delayed everolimus (introduced POD 30) with reduced dose tacrolimus (39% reduction of tacrolimus) showed comparable efficacy (incidence of biopsy proven acute rejection, graft loss or death) and had superior renal function as early as 1 month compared to standard dose tacrolimus. [23] Additionally, several small or retrospective studies have reported the use of everolimus in OLT recipients in combination with CNI reduction or as a CNI withdrawal strategy. [24-26]

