## Secondary Objectives

- Glomerular Filtration Rate (eGFR); Cockcroft and Gault (MDRD)
- To determine the incidence of confirmed acute rejection episodes in patients undergoing orthotopic liver transplant at 1, 3 and 6 months post-transplant
- To determine the tolerability and adverse event profile of basiliximab, delayed dose tacrolimus, mycophenolate mofetil, SOC corticosteroids and Everolimus during the first six months post-transplant
- To determine the incidence of infectious complications during the first six months post-transplant
- To determine the time to the first episode of acute rejection
- To determine the severity of each acute rejection episode
- To determine the incidence of death and/or graft failure within the first six months post-transplant
- To determine the number of patients requiring full dose CNI rescue therapy
- To determine the mean serum creatinine concentration and eGFR: Cockcroft and Gault (MDRD) at weeks 1, 2, 4, 8, 12, 16, 20 and 24 post OLT
- To monitor CD25 cell count for the first 3 months post-transplant
- Economic analysis to determine cost-effectiveness of induction therapy with IL-2 monoclonal antibody
- Economic analysis to determine cost-effectiveness of delayed therapy with everolimus

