## **Efficacy objectives at 1, 2, 3, and 5 months after start of everolimus**

To assess:

- Rate of composite efficacy failure of treated biopsy proven acute rejection (tBPAR), graft loss (GL) or death (D).
- Time to event and severity of tBPAR.
- Incidence and severity of all acute rejection.

To evaluate:

- Renal function over time assessed by mean change in eGFR by the Cockcroft and Gault (MDRD) from the start of everolimus.
- Urinary protein/creatinine ratio at various time points
- Incidence of and time to renal replacement therapy.

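### Rejection is compared only by tests for a difference, with no risk difference or confidence interval, so at 36 v 18 a non-significant result could not show adequate prevention

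*SAP*

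**What the plan says.** The SAP is one paragraph. For rates it states: "Categorical variables were expressed as a numerical percentage and compared by the Chi-square test or the Fishers Exact Test". For time-to-event data it plans Kaplan-Meier curves, and "differences in survival rates were analyzed using the Log-Rank test". All tests are two-sided at the 0.05 level. The Statistical analysis section of the protocol is still to be determined. Neither document gives a risk difference, confidence interval, margin, expected rejection rate or power calculation.

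The status of rejection varies within the protocol:

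- The synopsis Objectives compare the regimens "for prevention of acute organ rejection in liver transplant recipients with a high risk of developing renal dysfunction".
- The last paragraph of the Introduction counts rejection, graft loss and death in the primary objective, together with renal function.
- The synopsis Secondary Endpoints and the Secondary Objectives list rejection as secondary, for example "To determine the incidence of confirmed acute rejection episodes in patients undergoing orthotopic liver transplant at 1, 3 and 6 months post-transplant". The listed primary endpoint and primary objective are renal.
- The Efficacy objectives section adds a composite of treated biopsy-proven acute rejection (tBPAR), graft loss or death.

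Allocation is as follows: "In a 2:2:1 fashion, 90 subjects (group 1: n=36; group 2: n=36; group 3: n=18) will be randomized at UCLA Medical Center". Under Drug Therapy, Groups 1 and 2 start tacrolimus later than control and aim for 4-6 ng/mL, and Group 2 aims for 2-5 ng/mL from day 31. Control starts on day 1 at 5-12 ng/mL. Both experimental groups add basiliximab, and Group 2 also adds everolimus. The synopsis calls the study a pilot.

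**The concern.** The experimental regimens reduce tacrolimus exposure to protect the kidney and add other agents. A renal gain is useful only if rejection is not materially raised, so the question for rejection is how large an excess the data can rule out. A test for a difference does not answer that. Its non-significant result is compatible with no excess and with a large one, and with 18 controls it is the likely result in either case. Without an interval, the report would give two percentages and a p-value, and the reader could not tell which excesses remain possible.

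**Working it through.** **Inputs.** Group sizes 36, 36 and 18 (synopsis, Patient Population; 36 + 36 + 18 = 90, which matches 2:2:1). Two-sided 0.05; chi-square, Fisher or log-rank (SAP). Assumptions: control rates of 5% to 30%, because the documents give none; every patient evaluable; each experimental group compared separately with control. The plan states no power figure to reproduce.

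**Power.** All 19 x 37 possible tables were enumerated. Power is the sum, over tables with p<0.05, of Bin(a; 18, pc) x Bin(b; 36, pt), with the two-sided Fisher test or the uncorrected chi-square test.

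| Control rate | Doubled: Fisher / chi-square | Tripled: Fisher / chi-square |
|---|---|---|
| 5% | 1% / 3% | 7% / 12% |
| 10% | 9% / 12% | 32% / 36% |
| 15% | 17% / 20% | 55% / 61% |
| 20% | 25% / 30% | 81% / 82% |
| 25% | 38% / 41% | 95% / 95% |
| 30% | 53% / 54% | over 99% |

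Power passes 50% at a control rate of about 29% for a doubling, and at about 13% (chi-square) to 14% (Fisher) for a tripling. With a 10% control rate, Fisher needs about 48% in the experimental group for 80% power. For Group 2 v Group 1 (36 v 36), 10% v 20% is missed in 78% (chi-square) to 86% (Fisher) of trials.

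**Log-rank, if used for time to first rejection.** Schoenfeld approximation: power = Phi(sqrt(d x 1/3 x 2/3) x ln HR - 1.96).

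- 10% v 20%: d = 18 x 0.10 + 36 x 0.20 = 9.0; HR = ln 0.8 / ln 0.9 = 2.12; power 18%.
- 10% v 30%: d = 1.8 + 10.8 = 12.6; HR = ln 0.7 / ln 0.9 = 3.39; power 53%.

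**What an interval would show.** Newcombe 95% interval for d = p2 - p1, built from the Wilson limits (l, u) of each group: lower limit d - sqrt((p2 - l2)^2 + (u1 - p1)^2), upper limit d + sqrt((u2 - p2)^2 + (p1 - l1)^2). The Wilson limits for 2/18 are 0.031 and 0.328.

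- 4/36 v 2/18 (Wilson limits for 4/36: 0.044, 0.253): d = 0; lower limit -sqrt(0.067^2 + 0.217^2) = -0.227; upper limit sqrt(0.142^2 + 0.080^2) = +0.163.
- 8/36 v 2/18 (0.117, 0.381): d = +0.111; limits -0.130 and +0.289; Fisher p = 0.47.
- 12/36 v 2/18 (0.202, 0.497): d = +0.222; limits -0.031 and +0.404; Fisher p = 0.11.

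With 2/18 rejections in control, Fisher reaches p<0.05 only from 15/36 (42%).

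**Could a margin be met?** If both true rates are 10%, the upper limit falls below +10 points in 28% of trials and below +15 points in 46%. A non-inferiority test with a 10-point margin at a 10% rate (one-sided 0.025, 80% power) needs 7.849 x 0.10 x 0.90 x 1.5 / 0.10^2 = 106 controls. That means 212 per experimental group, or 530 in all.

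**The case against.** **No rule on interpretation.** A reader might infer that the investigators will report p>=0.05 as adequate prevention. The documents do not say so. The nearest text is the Introduction's account of an earlier 60-patient trial, which found a mild renal improvement "while maintaining adequate immunosuppression to prevent acute rejection". That trial used a different regimen, and its analysis is not shown. It shows why the safeguard is useful, not what will be done here.

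**Tripling.** A reader might also infer that even a tripled rate would usually be missed. That holds only below a control rate of about 13%. At 15%, chi-square or Fisher detects a tripling in 55-61% of trials, and log-rank detects it about half the time already at 10%.

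**Lower immunosuppression.** It is tempting to say that 72 of 90 patients receive less immunosuppression. Tacrolimus is delayed and lowered, but basiliximab and everolimus are added, so the net direction is not established.

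**Pilot, secondary endpoint.** The formal primary endpoint is renal, the objectives speak of assessing and determining incidence, and no comparability claim is proposed. This excuses the low power and is a good reason not to demand a non-inferiority margin, which the trial would seldom meet. It does not turn a non-significant test into evidence of similarity, and a pilot is where estimates with intervals serve best.

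**Conclusion.** The point holds as a gap in analysis and reporting. The SAP plans only tests for a difference on rejection, and neither document plans an estimate that shows how much excess rejection remains possible. At 36 v 18 a doubled rate would usually be non-significant by chi-square or Fisher for control rates up to about 28%, and a tripled rate also below about 13%. These figures rest on assumed control rates, complete data and pairwise comparisons; patients lost to follow-up would lower the power further. So p>=0.05 could not support a statement that the experimental regimens prevent rejection adequately. It does not follow that the regimens raise rejection or that the investigators intend to make that statement.

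**What to change.** Add to the SAP, for the composite of tBPAR, graft loss or death and for acute rejection:

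1. The risk difference with a two-sided 95% confidence interval (Newcombe or Miettinen-Nurminen) for Group 1 v 3, Group 2 v 3 and Group 2 v 1.
2. A statement that p>=0.05 will not be read as comparable or adequate prevention.
3. The largest excess that the interval does not exclude, reported with each comparison.

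No non-inferiority margin is required. If the investigators want to claim comparability, they should fix the acceptable excess in writing before they see comparative data. If such data have already been seen, items 1 to 3 can still be done in full.

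The cost is a short SAP paragraph and a few table entries (three comparisons for two endpoints), with no extra patients or visits. The downside is that the rejection result will probably read as inconclusive.
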